- Placebo (0.9% saline) as Dose 1 on Day 1, followed by placebo as Dose 2 on Day 57, followed by placebo as booster dose on Day 177 (booster dose for Group 6 only).

All participants will sign the informed consent form (ICF) and will be screened for eligibility at baseline (Day 1), which is also the day of Dose 1 vaccination. If needed, the screening activities

may be split over multiple visits, with a maximum time of up to 28 days between signing of the ICF and Dose 1 vaccination. Dose 2 vaccination will be given on Day 57. Participants in the immunogenicity subset and in Groups 5-6 will be followed for immunogenicity until the 21-day post Dose 2 visit (Day 78). Participants in Groups 5-6 will in addition be followed up from pre booster dose (Day 177) until 12 months after receiving the booster dose (Day 537). Samples for immunogenicity assessments will be taken pre Dose 1 (Day 1), pre Dose 2 (Day 57), 21 days post Dose 2 (Day 78), and in Groups 5-6 also pre booster dose (Day 177), and 7 days (Day 184), 21 days (Day 198), 6 months (Day 357), and 12 months (Day 537) after the booster dose. All participants will complete diary cards until 7 days post each vaccination (solicited adverse events), which will be reviewed by study site personnel at the Day 57 visit (before Dose 2 vaccination), at the Day 78 visit, and at the Day 184 visit (Groups 5-6 only). Unsolicited adverse events will be recorded until 28 days post each vaccination; participants will be asked about these at the Day 57 visit, at the Day 78 visit, at the Day 177, 184 and 198 visits (Groups 5-6 only), and by means of a telephone call at Days 29 and 85, and at Day 205 (Groups 5-6 only). Serious adverse events will be recorded until the end of the study with a telephone call foreseen for Groups 1-4 only at 6 months post Dose 2 (Day 237).

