10. PARTICIPANT COMPLETION/DISCONTINUATION OF STUDY VACCINE/ WITHDRAWAL FROM THE STUDY

10.1. Completion

A participant in Groups 1-4 will be considered to have completed the study if he or she has completed assessments at the Day 237 time point (ie, 6-months post Dose 2). A participant in Groups 5-6 will be considered to have completed the study if he or she has completed assessments at the Day 537 time point (ie, 12-months post booster dose).

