### **5. SAFETY**

Safety analyses will be performed on the full analysis set. Frequencies and percentages (one decimal place) will be generated for the AEs. No formal comparisons between groups will be provided.

The safety data will be presented by vaccination group (as shown in [Table 2](#)). The data will be presented by analysis period (post-dose 1, post-dose 2, and post-booster [only for the booster cohort]) as well as over the entire regimen period (ie, combined post-dose 1 and post-dose 2 periods, and combined post-dose 1, post-dose 2 and post-booster [only for the booster cohort]). Denominator for the percentages will be the

number of participants in the considered analysis set and period/phase for a certain vaccination group (eg, incidence per 100 participants/period).

To evaluate the potential impact of delayed (due to COVID-19 pandemic) Dose 2 vaccination, safety data will also be presented (only if more than 10% of participants receive Dose 2 vaccination outside the widened window) for participants having received Dose 2 vaccination within the widened window (as defined in CTP Amendment 3) versus those having received Dose 2 outside the window.

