### 5.1.1. Definitions

Solicited AEs shown in the tables will be extracted from the investigator assessment pages of the eCRF. The severity of all AEs will be classified as Grade 1 to 3. For unsolicited AEs, only the AEs within the 28-day period following each vaccination will be presented in the safety tables except for SAEs which will be captured and tabulated covering the entire study duration. A listing will also be generated for all collected unsolicited AEs.

Solicited local AEs will be considered (by definition) as related to the study vaccine. In case no grades are available, the grading of the solicited events will occur according to the grading list in Attachment 1.

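### At the final analysis, whole-study SAE percentages for Groups 5-6 (followed to about Day 537) are not comparable with those for Groups 1-4 (followed to about Day 237), and no person-time rate or common cut-off is planned

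*Protocol*

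**What the plan says.** **Collection.** Protocol 3.1 says: "Serious adverse events will be recorded until the end of the study with a telephone call foreseen for Groups 1-4 only at 6 months" after Dose 2. Under Protocol 10.1, Groups 1-4 complete the study when they have "completed assessments at the Day 237 time point (ie, 6-months post Dose 2"). For the booster cohort the same section says: "A participant in Groups 5-6 will be considered to have completed the study if he or she has completed assessments at the Day 537", which is 12 months after the booster.

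**Tabulation.** SAP 5.1.1 limits the tables of unsolicited events to 28 days after each dose, "except for SAEs which will be captured and tabulated covering the entire study duration". SAP 5 sets the measure: "Frequencies and percentages (one decimal place) will be generated for the AEs. No formal comparisons between groups will be provided". The denominator is the "number of participants in the considered analysis set and period/phase for a certain vaccination group", so it counts people and not time. The columns are the six groups of SAP Table 2.

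**Periods.** SAP 5 also states: "The data will be presented by analysis period (post-dose 1, post-dose 2, and post-booster [only for the booster cohort"]), plus the combined regimen. Each of these periods lasts at most 28 days (SAP Table 3).

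**What is not listed.** The AE outputs in SAP 5.1.2 include SAEs and related SAEs, but no rate per unit of time and no table with a common end day. SAP 4.2 counts participants in each analysis period. It does not tabulate follow-up time.

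**The concern.** An SAE percentage over the whole study rises with the length of observation. Here that length differs by design between groups that share one table. Group 5 receives the same primary regimen as Groups 1-3 and then a booster, so its column invites comparison with the 702 recipients in Groups 1-3. Its randomised control, Group 6, has only about 10 participants and gives little to compare with. Protocol 1.3 says there are no clinical data on this booster given less than a year after the primary regimen, and SAEs to the end of the study are a stated (exploratory) booster endpoint. A higher SAE percentage in Group 5 that came only from longer follow-up could be read as a booster effect.

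The 28-day period tables are like for like but leave out later SAEs. The follow-up periods in SAP Table 3 would not help if tabulated, because they differ too. Post-dose 2 follow-up lasts about 237 − 85 = 152 days in Groups 1-4 and about 177 − 85 = 92 days in Groups 5-6. Post-dose 3 follow-up (about 537 − 205 = 332 days) exists only in Groups 5-6.

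**Working it through.** **Inputs**
- End of follow-up: Day 237 and Day 537 (Protocol 10.1).
- Windows: Day 237 ±15 days, Day 537 ±4 weeks, Dose 2 in Groups 1-4 from Day 54 to Day 85 (Time and Events Schedule).
- Sizes: 3 × 234 = 702 in Groups 1-3, about 50 in Group 5, about 10 in Group 6 (Protocol Table 1).
- Illustrative base risk: 2.2%, the SAE percentage on both active vaccine and placebo in earlier studies (Protocol 1.1). Its follow-up time is not given, so using it as the risk to Day 237 is an assumption, and a range is shown.

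**1. The schedule reproduces.** With 30-day months: 57 + 180 = 237; 57 + 120 = 177; 177 + 360 = 537. From Dose 1 on Day 1, follow-up is 236 and 536 days, a ratio of 536/236 = 2.27.

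**2. Expected percentages with a constant hazard and no booster effect.** If p is the risk to Day 237, the risk to Day 537 is 1 − (1 − p)^(536/236).

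| Risk to Day 237 | Risk to Day 537 | Ratio |
|---|---|---|
| 0.5% | 1.13% | 2.26 |
| 1% | 2.26% | 2.26 |
| 2.2% | 4.93% | 2.24 |
| 5% | 11.00% | 2.20 |
| 10% | 21.28% | 2.13 |

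The ratio stays above 2 for base risks below about 19%. It hardly depends on what the 2.2% refers to: if it were a one-year risk, the two percentages would be 1.43% and 3.21% (ratio 2.25). At 2.2% to Day 237, Group 5 would expect 50 × 4.93% = 2.5 participants with an SAE, against 50 × 2.2% = 1.1 at equal follow-up.

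**3. Departures from the nominal schedule and the constant hazard (2.2% base)**
- Visit windows: 2.0 (Day 252 against 509) to 2.5 (Day 222 against 565).
- Dose 2 at Day 85, which moves the last contact to 85 + 180 = Day 265: 2.0. At the extreme (Day 280 against 509): 1.8.
- Hazard k times higher for 28 days after Doses 1 and 2, with no rise after the booster. The ratio of cumulative hazards, which percentages follow closely at low risk, is (480 + 56k)/(180 + 56k). For k = 2 it is 592/292 = 2.03, and for k = 5 it is 760/460 = 1.65.

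**4. Chance.** With 50 against 702 participants and a 2.2% base, the observed Group 5 percentage exceeds twice the pooled Groups 1-3 percentage with probability about 0.55. At equal follow-up the probability would be 0.18. Group 5 has no SAE at all with probability about 0.08. Group 6 expects 10 × 4.93% = 0.5 participants with an SAE and has none with probability 0.60.

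**5. Booster-cohort interim.** At 28 days after the booster (177 + 28 = Day 205), set against Day 237 in Groups 1-4, the expected ratio is about 0.87.

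**6. After the change.** The hazard is −ln(1 − 0.022)/236 = 0.094 per 1,000 person-days in both sets of groups, so the expected rate ratio is 1.00. A common cut at Day 237 also gives 1.00.

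**The case against.** A reader might infer that the boosted group will show over twice the SAE percentage even if the booster does nothing. The documents do not support that. They state no hazard, the expected ratio falls to 2 or below in several plausible settings, and with 50 participants an observed doubling is close to a coin toss.

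Nor do the documents plan a comparison of Group 5 with Groups 1-3. Booster safety is an exploratory objective of the booster cohort, and SAP 5 rules out formal comparisons, although Protocol 11.4 allows between-group comparisons of adverse events where appropriate. Groups 5-6 are randomised separately and later, so a contrast with Groups 1-4 is non-randomised, and rates per person-year would not make it randomised. The randomised comparator, Group 6, has the same follow-up as Group 5. The interim at about Day 205 shows no excess from follow-up length. With one to three expected cases, the onset date relative to the booster tells most, and SAP 5.1.2 already provides listings and/or narratives for participants with an SAE.

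All of this stands, and it limits the point to the final analysis and to the comparability of columns. It does not remove the point. Descriptive tables are the only planned safety evidence, and these columns cover unequal time without saying so. Allocating late SAEs to follow-up periods helps only in part, because SAP 5 does not list those periods among the ones presented.

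**Conclusion.** The point holds as a matter of presentation. At the final analysis the whole-study SAE percentages of Groups 5-6 and Groups 1-4 are not comparable, because follow-up differs about 2.27-fold and no planned output allows for it. The expected ratio with no booster effect is about 2.2 under a constant hazard, and 1.65 to 2.5 across the scenarios tested. All of these lie above 1, so at the final analysis the distortion runs against the booster. The size rests on the assumed hazard shape and only slightly on the base risk. The incomparability itself rests on the schedule alone.

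The immunogenicity hypotheses are untouched. This is a low-priority improvement and not a fault in the trial's main conclusions.

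**What to change.** In SAP 5.1.2:
1. Keep the SAE percentages and add total follow-up time by group.
2. Add SAE rates (all and related) per 100 person-years with exact Poisson 95% CIs by group. State whether the numerator is participants with a first SAE, with time counted to that event or to the end of follow-up.
3. Add one SAE table for all six groups cut at a common day. Day 237 suits, since it includes 237 − 177 = 60 days after the booster. A cut before the booster would contain no post-booster time and could not inform on it.
4. Add a footnote that Group 6 is the randomised comparator for Group 5, with equal follow-up, and that contrasts with Groups 1-4 are non-randomised.

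The dates needed are already collected, and no visit or sample size changes. The cost is programming. The rates will be imprecise: Group 5 contributes about 50 × 536/365.25 = 73 person-years, so two participants with an SAE would give 2.7 per 100 person-years with a 95% CI of about 0.3 to 9.8. Groups 5-6 were not yet recruited at Amendment 3, so the change could have been specified before any booster data existed.

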3.2. Study Design Rationale

Control and Blinding

A placebo control will be used to establish the frequency and magnitude of changes in clinical endpoints that may occur in the absence of active study vaccine. Randomization will be used to minimize bias in the assignment of participants to vaccination groups, to increase the likelihood that known and unknown participant attributes (eg, demographic and baseline characteristics) are evenly balanced across vaccination groups, and to enhance the validity of statistical comparisons across vaccination groups. Blinded vaccination will be used to reduce potential bias during data collection and evaluation of clinical endpoints.

Vaccination Groups

Groups 1, 2, and 3 will only differ in the lots of the study vaccine, while the dose of each vaccine and the sequence of vaccination will be identical. For Groups 1, 2, 3 and 5, Dose 1 consists of Ad26.ZEBOV at a nominal dose of 5×10^{10} vp and Dose 2 consists of MVA-BN-Filo at a nominal dose of 1×10^8 Inf U. For Group 5, the booster dose consists of Ad26.ZEBOV at a nominal dose of 5×10^{10} vp from a single lot. Groups 4 and 6 will receive placebo.

4. PARTICIPANT POPULATION

Screening for eligible participants will be performed at baseline (Day 1), which is also the day of Dose 1 vaccination. If needed, the screening activities may be split over multiple visits, with a maximum time of up to 28 days between signing of the ICF and Dose 1 vaccination.

The inclusion and exclusion criteria for enrolling participants in this study are described in the following 2 subsections. If there is a question about the inclusion or exclusion criteria below, the investigator must consult with the appropriate sponsor representative and resolve any issues before enrolling a participant in the study. Waivers are not allowed.

For a discussion of the statistical considerations of participant selection, refer to Section 11.2.

4.1. Inclusion Criteria

Each potential participant must satisfy all of the following criteria to be enrolled in the study:

1. Signed an ICF indicating that he or she understands the purpose of, and procedures required for, the study as well as the potential risks and benefits of the study, and is willing to participate in the study.
2. Man or woman, 18 to 50 years of age, inclusive, on the day of signing the ICF.

3. Medically stable in the investigator's clinical judgment on the basis of physical examination, medical history, and vital signs performed at screening.
4. Criterion modified per Amendment 2
 - 4.1 Before randomization, a woman must be either:
 - a. Not of childbearing potential;
 - b. Of childbearing potential and practicing an acceptable effective method of birth control and agrees to remain on such a method of birth control from signing the ICF until at least 3 months post Dose 1 vaccination or 28 days post Dose 2 vaccination or 3 months post booster vaccination (Groups 5-6 only), whichever comes later. Use of hormonal contraception should start at least 28 days before the first administration of study vaccine. Acceptable effective methods for this study include:
 - 1) hormonal contraception;
 - 2) intrauterine device (IUD);
 - 3) intrauterine hormone-releasing system (IUS);
 - 4) male or female condom with or without spermicide;
 - 5) cap, diaphragm, or sponge with a vaginal spermicide;
 - 6) vasectomized partner (the vasectomized partner should be the sole partner for that participant);
 - 7) sexual abstinence*.
- *Sexual abstinence is considered an effective method **only** if defined as refraining from heterosexual intercourse from signing the ICF until at least 3 months post Dose 1 vaccination or 28 days post Dose 2 vaccination, whichever comes later. The reliability of sexual abstinence needs to be evaluated in relation to the duration of the study and the preferred and usual lifestyle of the participant.
5. Women of childbearing potential must have a negative urine β -hCG pregnancy test at screening and immediately prior to each study vaccine administration.
6. Available and willing to participate for the duration of the study and follow-up visit.
7. Willing and able to comply with the protocol requirements, including the prohibitions and restrictions specified in Section 4.3.
8. Willing to provide verifiable identification.
9. Having a means to be contacted.

Contraceptive (birth control) use by women should be consistent with local regulations regarding the acceptable methods of birth control for those participating in clinical studies.

Typical use failure rates may differ from those when used consistently and correctly. Use should be consistent with local regulations regarding the use of birth control methods for participants in clinical studies.

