In general, uninfected participants who are taking part in Ebola vaccine studies may develop Ebola-specific antibodies as a result of an immune response to the candidate Ebola vaccine, referred to as vaccine-induced seropositivity (VISp). These antibodies may be detected in Ebola serologic tests, causing the test to appear positive even in the absence of actual Ebola infection. VISp may become evident during the study, or after the study has been completed. The potential of a participant becoming PCR-positive after vaccination was assessed in study VAC52150EBL1002. None of the participants tested positive for EBOV after vaccination.

Consent will be obtained to contact the doctors that the participant sees regularly, to let them know that the participant is taking part in this study. It is important for all of the participant's doctors to know that the participant may be administered experimental vaccines. Participants will be provided with a "wallet (study) card" and instructed to carry this card with them for the duration of the study (see Section [12.3.1](#)).

Pregnancy and Birth Control

The effect of the vaccines on a fetus or nursing baby is unknown. Female participants of childbearing potential will be required to agree to use birth control for sexual intercourse beginning 28 days prior to vaccination and continuing until at least 3 months post Dose 1 vaccination, 28 days post Dose 2 vaccination, or 3 months post booster vaccination (Groups 5-6 only), whichever comes later. Women who are pregnant or breast-feeding may not receive further study vaccines but may continue other study procedures at the discretion of the investigator.

Male participants should inform the investigator and the sponsor in case their partner would become pregnant during the study.

Unknown Risks

There may be other risks that are not known. If any significant new risks are identified, the investigator and participants will be informed.

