4.2. Exclusion Criteria

Any potential participant who meets any of the following criteria will be excluded from participating in the study:

1. Having received any candidate Ebola vaccine.
2. Diagnosed with EVD, or prior exposure to Ebola virus, including travel to an area with Ebola outbreak less than 1 month prior to screening (if applicable).
3. Having ever received any experimental candidate Ad26- or MVA-based vaccine in the past.
4. Known allergy or history of anaphylaxis or other serious adverse reactions to vaccines or vaccine products (including any of the constituents of the study vaccines), including known allergy to chicken or egg protein and gentamicin.
5. Presence of acute illness (this does not include minor illnesses such as diarrhea or mild upper respiratory tract infection) or temperature $\geq 38.0^{\circ}\text{C}$ on Day 1. Participants with such symptoms will be excluded from enrollment at that time but may be rescheduled for enrollment at a later date.
6. HIV type 1 or type 2 infection, based on the medical history reported by the participant.
7. Criterion modified per Amendment 1
 - 7.1 Criterion modified per Amendment 2
 - 7.2 Pregnant, breast-feeding, or planning to become pregnant while enrolled in this study until at least 3 months post Dose 1 vaccination, 28 days post Dose 2 vaccination, or 3 months post booster vaccination (Groups 5-6 only), whichever comes later.
8. Major surgery (per the investigator's judgment) within the 4 weeks prior to screening or planned major surgery during the study (from the start of screening onwards). Participants with planned surgical procedures to be conducted under local and loco-regional anesthesia may participate.
9. Post-organ and/or stem cell transplant whether or not with chronic immunosuppressive therapy.
10. Received any disallowed therapies as noted in Section 8 before the planned administration of Dose 1.
11. Received an investigational drug or investigational vaccine or used an invasive investigational medical device within 3 months prior to screening, or current or planned participation in another clinical study during the study.

Note: Participation in an observational clinical study is allowed.

12. Criterion modified per Amendment 2

12.1 Received or plans to receive:

- a. Licensed live-attenuated vaccines within 28 days before or after planned administration of the first or second study vaccine or booster dose (Groups 5-6 only);

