4.3. Prohibitions and Restrictions

Potential participants must be willing and able to adhere to the following prohibitions and restrictions during the course of the study to be eligible for participation:

1. Women of childbearing potential must remain on an acceptable effective method of birth control consistent with local regulations regarding the use of birth control methods for participants in clinical studies (see inclusion criteria in Section 4.1) until at least 3 months post Dose 1 vaccination or 28 days post Dose 2 vaccination or 3 months post booster vaccination (Groups 5-6 only), whichever comes later. If the social situation of a woman of childbearing potential changes (eg, woman who is not heterosexually active becomes active), she must begin a highly effective method of birth control, as described above in Section 4.1, until at least 3 months post Dose 1 vaccination or 28 days post Dose 2 vaccination or 3 months post booster vaccination (Groups 5-6 only), whichever comes later.

Note: Prior to each study vaccine administration, a urine pregnancy test should be performed for women of childbearing potential.

2. In case of a new Ebola outbreak: participants should not travel to an area with Ebola outbreak while enrolled in the study from the start of screening onwards until the 21-day post Dose 2/booster dose (Groups 5-6 only) visit. If applicable, any traveling to an area with Ebola outbreak should be documented in the electronic case report form (eCRF).
3. Refer to Section 8 for details regarding prohibited and restricted therapy during the study.
4. Agree to follow all requirements that must be met during the study as noted in the inclusion and exclusion criteria (eg, contraceptive requirements).

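### The abstinence footnote in inclusion criterion 4 ends before the booster dose, while the criterion it qualifies and three other sections run to 3 months after the booster for Groups 5-6

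*Protocol*

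**What the plan says.** Inclusion criterion 4 in Protocol Section 4.1 carries the label "Criterion modified per Amendment 2". Item b requires a woman of childbearing potential to stay on an acceptable method from consent to the latest of three dates. The third of these is "3 months post booster vaccination (Groups 5-6 only), whichever comes later".

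Abstinence is method 7 in the list under item b, and a footnote defines it. It counts only if it means "refraining from heterosexual intercourse from signing the ICF until at least 3 months post Dose 1 vaccination or 28 days post Dose 2 vaccination", and the sentence then closes with the later-of rule. No booster term follows. The next sentence adds: "The reliability of sexual abstinence needs to be evaluated in relation to the duration of the study".

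Three other places state the period with the booster term:

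- Section 1.2.4 describes birth control "continuing until at least 3 months post Dose 1 vaccination, 28 days post Dose 2 vaccination, or 3 months post booster vaccination" for Groups 5-6.
- Exclusion criterion 7.2 bars planned pregnancy up to the latest of three dates, ending "28 days post Dose 2 vaccination, or 3 months post booster vaccination (Groups 5-6 only), whichever comes later".
- Section 4.3 item 1 gives the same three dates twice. The second time concerns a change in circumstances: "woman who is not heterosexually active becomes active), she must begin a highly effective method of birth control".

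Inclusion criterion 5 requires a negative urine pregnancy test "at screening and immediately prior to each study vaccine administration".

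**The concern.** The footnote is definitional: abstinence is acceptable only if it covers the stated period. Staff counselling a woman who relies on abstinence would naturally look there for her end date. For Groups 5-6 that date falls before the booster, so the period covers neither the third vaccination nor the 3 months after it. The documents give no reason why abstinence should end earlier than any other method. The reason for contraception in Section 1.2.4, that effects on a fetus or nursing baby are unknown, applies to all methods alike.

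Two things are at stake, both small. The first is fetal exposure: the test before the booster detects an existing pregnancy but does nothing about conception afterwards. The second is loss of data: under Section 10.2 a woman who becomes pregnant before the booster must permanently stop study vaccine. She would then drop out of the Booster Cohort per protocol set, which requires the booster (Protocol Section 11.1, SAP Section 2.3.2).

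**Working it through.** The plan states no figure to reproduce. The check is a comparison of texts followed by a day count.

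**Texts side by side**

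| Place in the Protocol | Dose 1 term | Dose 2 term | Booster term (Groups 5-6) |
|---|---|---|---|
| 4.1, criterion 4.1b | 3 months | 28 days | 3 months |
| 4.1, abstinence footnote | 3 months | 28 days | none |
| 1.2.4 | 3 months | 28 days | 3 months |
| 4.2, exclusion 7.2 | 3 months | 28 days | 3 months |
| 4.3, item 1 (twice) | 3 months | 28 days | 3 months |

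The footnote is the only one that differs.

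**Inputs**

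- Vaccination days for Groups 5-6: Days 1, 57 and 177 (Section 6).
- Windows for Groups 5-6: Dose 2 and booster each ±1 week (Time and Events Schedule).
- Assumption: 3 months is 90 to 92 days, since the protocol does not convert it. The 90-day end fits the protocol's own use of 4 months for Day 57 to Day 177: 177 − 57 = 120 days.

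**Nominal schedule**

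1. Footnote end = max(1 + 3 months, 57 + 28) = max(91 to 93, 85) = Day 91 to 93.
2. Time from footnote end to booster = 177 − 91 = 86 days down to 177 − 93 = 84 days, about 12 weeks.
3. Criterion 4.1b end = 177 + 3 months = Day 267 to 269.
4. Difference between the two texts = 267 − 91 = 268 − 92 = 269 − 93 = 176 days.

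**With the visit windows** (3 months as 90 days, no postponement)

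1. Dose 2 falls on Day 50 to 64, so Dose 2 + 28 is Day 78 to 92, and the footnote ends at max(91, 78 to 92) = Day 91 to 92.
2. The booster falls on Day 170 to 184, so 4.1b ends at Day 260 to 274.
3. The difference is about 260 − 92 = 168 to 274 − 91 = 183 days.

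**Groups 1-4.** Both texts reduce to the later of Dose 1 + 3 months and Dose 2 + 28 days. The difference is 0.

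**Who could be concerned.** The Booster Cohort is 60 of at least 741 + 60 = 801 planned participants, and 60/801 = 7.5%. That is a ceiling. It includes men, women not of childbearing potential and women using another method. The documents do not give the number relying on abstinence, and it could be zero.

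**The case against.** The strongest reply is that other text already covers this woman. The footnote qualifies one method in a list and does not set the contraception period. Criterion 4.1b sets it, and runs to 3 months after the booster. Section 4.3 item 1 deals directly with a woman who was not heterosexually active and becomes so, and holds her to the same date. Inclusion criterion 7 makes compliance with Section 4.3 a condition of entry, and exclusion 7.2 bars planned pregnancy over the same period. A test precedes each dose, and Section 4 sends eligibility questions to the sponsor before enrollment.

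The footnote also sets a minimum, so a woman who follows 4.1b breaches neither text. Its next sentence points to the duration of the study, which for Groups 5-6 runs to Day 537 (Section 10.1). What participants are actually told is in the consent form, which is not available here and may already give the booster date.

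Most of this stands. There is no gap in the obligation, and harm requires a site to rely on the footnote alone. It does not make the text consistent, however. A minimum that expires before the booster is the wrong minimum, and the sentence on study duration supplies no replacement date. Consulting the sponsor helps only if a site notices the conflict. The consent form cannot be assessed either way.

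The cause is also an inference. The amendment history lists Section 4.1 among the sections changed for the Booster Cohort, and the footnote has only two-dose wording, so a missed conforming edit is the likely explanation. The text before Amendment 2 is not shown. The mismatch in the current text does not depend on its origin.

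**Conclusion.** The concern holds as a minor internal inconsistency in current eligibility text. For Groups 5-6 the abstinence definition ends about 12 weeks before the booster on the nominal schedule and 176 days before the date in the criterion it belongs to. These counts rest on taking 3 months as 90 to 92 days. They measure the wording and do not represent a period in which participants are released from contraception.

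No design decision is in question. The primary and secondary equivalence tests, the sample size and the power are untouched, and the Booster Cohort objectives are exploratory. Correcting the text brings a small gain in participant protection.

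**What to change.** In the abstinence footnote of Protocol Section 4.1, after the Dose 2 term, replace the closing words so that the sentence ends: or "3 months post booster vaccination (Groups 5-6 only), whichever comes later". This is the wording of criterion 4.1b. The footnote's nominal end for Groups 5-6 then becomes Day 267 to 269, matching 4.1b, and nothing changes for Groups 1-4.

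Section 3.1 says Groups 5 and 6 have not yet been recruited, so the change can be in place before anyone it concerns enrolls. The cost is one clause, with no effect on visits, sample size or analysis. The Booster Cohort consent form should be checked for the same end date at the same time.
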